11.6.2 Safety Data

Summaries and analysis of safety data will be presented for the Safety Analysis Population. All summaries and analyses will be presented for all subjects.

Solicited AEs will be summarized by severity for each day after study vaccination (Days 1-8 post study vaccination) and as the maximum severity over all 8 days. Additionally, solicited AEs will be analyzed by taking the most severe response over the follow-up period, dichotomizing into a binary variable (none versus mild, moderate or severe) and using standard techniques, such as exact CIs, to summarize the proportion of subjects reporting each symptom, any injection site symptom and any systemic symptom. The proportion of subjects reporting symptoms may be compared between treatment arms using Chi-square or Fisher's exact test.

Unsolicited AEs will be coded by Medical Dictionary for Regulatory Activities (MedDRA[®]) for preferred term (PT) and system organ class (SOC). The numbers of SAEs and MAAEs, including NOCMCs and PIMMCs, are likely to be small in this trial and will be reported by detailed listings showing the event description, MedDRA[®] PT and SOC, relevant dates (study vaccinations and AEs), severity, relatedness, and outcome for each event. Non-serious unsolicited AEs will be summarized as number and percentage of subjects reporting at least one event in each MedDRA[®] PT and SOC, cross-tabulated by severity and relationship to study product. Additionally, the proportion of subjects and exact 95% CIs of AEs in aggregate and by MedDRA[®] categories will be computed.

Clinical laboratory data will be summarized by severity for each visit and as the maximum over all post-study vaccination visits. Graphical presentations may include box plots.

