### **3.2.2. Secondary**

#### Safety:

- Occurrence of all unsolicited non-serious AEs from the time of study vaccination through approximately 21 days after study vaccination.
- Occurrence of all MAAEs, including NOCMCs and PIMMCs from the time of study vaccination through approximately 12 months after study vaccination.

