##### **4.5.1. Safety Variables**

Safety will be assessed by the frequency and severity:

1. SAEs occurring from the time of study vaccination through approximately 12 months after study vaccination.
2. Solicited AEs – reactogenicity events occurring from the time of study vaccination through 7 days after study vaccination:
  - a. Injection site reactions including pruritus, ecchymosis, erythema, induration/edema, pain, and tenderness.
  - b. Systemic reactions including fever, feverishness, fatigue, malaise, myalgia, arthralgia, headache, and nausea.
3. Clinical safety laboratory AEs occurring from the time of study vaccination through approximately 7 days after study vaccination. Parameters to be evaluated include white blood cell (WBC) count, hemoglobin (Hgb), platelets (PLT), alanine aminotransferase (ALT), total bilirubin (Bili), and creatinine (Cr).
4. Vital sign AEs occurring from the time of study vaccination through approximately 7 days after study vaccination. Parameters to be evaluated include pulse, systolic and diastolic blood pressures, and oral temperature.
5. Unsolicited AEs – non-serious AEs occurring from the time of study vaccination through approximately 21 days after study vaccination.
6. MAAEs, including NOCMCs and PIMMCs, occurring from the time of study vaccination through approximately 12 months after study vaccination.

Grading scales for injection site and systemic solicited reactions, vital signs, and clinical laboratory parameters are provided in [Table 9](#), [Table 10](#), [Table 11](#), and [Table 12](#).

For each unsolicited AE experienced, the subject will be asked if he/she had received medical attention, defined as hospitalization, an emergency room visit or an otherwise unscheduled visit to or from medical personnel for any reason. AEs characterized by such unscheduled medical care will be designated as MAAEs.

NOCMCs are defined as any new ICD-10 diagnosis (10th revision of the International Statistical Classification of Diseases and Related Health Problems) that is applied to the subject during the course of the study, after receipt of the study agent, that is expected to continue for at least 3 months and requires continued health care intervention.

PIMMCs constitute a group of AEs that includes diseases which are clearly autoimmune in etiology and other inflammatory and/or neurologic disorders which may or may not have autoimmune etiologies. For a list of PIMMCs currently in effect, refer to protocol Appendix B.

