#### 9.3.2. Unsolicited Adverse Events

When calculating the incidence of unsolicited AEs (i.e., on a per subject basis), each subject will only be counted once at the highest severity and/or relationship, and any repetitions of AEs within a subject will be ignored. The denominator for these summaries will be the total number of subjects in the Safety population. All AEs reported will be included in the summaries and analyses.

The number and percentage of subjects reporting at least one unsolicited AE in each stratum and study group will be summarized by MedDRA system organ class (SOC) and preferred term (PT). A 95% CI will be

presented for the percentage of subjects reporting any unsolicited event (serious or non-serious) for each MedDRA SOC and PT in [Table 53](#).

The following summaries for unsolicited AEs will be presented by MedDRA SOC, PT, study group, and stratum:

- Incidence of AEs by severity and relationship to study product in [Table 54](#);
- Incidence of non-serious, related AEs by severity in [Table 55](#);
- Incidence of AEs over time (Days 1-8, Days 9-22 post study vaccination) in [Table 56](#);
- Incidence of non-serious, related AEs over time (Days 1-8, Days 9-22 post study vaccination) in [Table 57](#) – note this table presents results for the secondary safety endpoint, “Occurrence of study vaccine-related unsolicited non-serious AEs from the time of study vaccination through approximately 21 days after study vaccination”;
- Total frequency of AEs over time (Days 1-8, Days 9-22 post study vaccination) in [Table 58](#);
- Subject listing of non-serious AEs of moderate or great severity in [Table 63](#);
- Bar chart displaying total frequency of AEs by severity, MedDRA SOC, study group, and stratum in [Figure 28](#);
- Bar chart displaying incidence of AEs by severity, MedDRA SOC, study group, and stratum in [Figure 29](#);
- Bar charts displaying total frequency and incidence of AEs by relationship to study product, MedDRA SOC, study group, and stratum in [Figure 30](#) and [Figure 31](#), respectively;

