## **11. TECHNICAL DETAILS**

SAS version 9.4 or above will be used to generate all tables, figures and listings.

**12. SUMMARY OF CHANGES IN THE CONDUCT OF THE STUDY OR  
PLANNED ANALYSES**

This SAP does not include any changes from the analyses described in the protocol.

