**14.3.1.2 Unsolicited Adverse Events**

**Table 53: Number and Percentage of Subjects Experiencing Unsolicited Adverse Events with 95% Confidence Intervals by MedDRA System Organ Class and Preferred Term, Stratum and Study Group, Safety Population**

MedDRA System Organ Class	MedDRA Preferred Term	2013 A/H7N9 IIV + MF59 (N=X)		2013 A/H7N9 IIV + AS03 (N=X)		2013 A/H7N9 IIV 15 mcg or 45 mcg unadjuvanted (N=X)		2013 A/H7N9 IIV with MF59/AS03 then 2013 A/H7N9 IIV 15 mcg (N=X)		A/H7 IIV Naïve (N=X)		All Subjects (N=X)	
		n	% (95% CI)	n	% (95% CI)	n	% (95% CI)	n	% (95% CI)	n	% (95% CI)	n	% (95% CI)
3.75 mcg A/H7N9 IIV													
Any SOC	Any PT	x	xx (xx-xx)	x	xx (xx-xx)	x	xx (xx-xx)	x	xx (xx-xx)	x	xx (xx-xx)	x	xx (xx-xx)
[SOC 1]	Any PT												
	[PT 1]												
	[PT 2]												
[SOC 2]	Any PT												
	[PT 1]												
	[PT 2]												
3.75 mcg A/H7N9 IIV + AS03													
Any SOC	Any PT	x	xx (xx-xx)	x	xx (xx-xx)	x	xx (xx-xx)	x	xx (xx-xx)	x	xx (xx-xx)	x	xx (xx-xx)
[SOC 1]	Any PT												
	[PT 1]												
	[PT 2]												
[SOC 2]	Any PT												
	[PT 1]												
	[PT 2]												
All Subjects													

MedDRA System Organ Class	MedDRA Preferred Term	2013 A/H7N9 IIV + MF59 (N=X)		2013 A/H7N9 IIV + AS03 (N=X)		2013 A/H7N9 IIV 15 mcg or 45 mcg unadjuvanted (N=X)		2013 A/H7N9 IIV with MF59/AS03 then 2013 A/H7N9 IIV 15 mcg (N=X)		A/H7 IIV Naïve (N=X)		All Subjects (N=X)	
		n	% (95% CI)	n	% (95% CI)	n	% (95% CI)	n	% (95% CI)	n	% (95% CI)	n	% (95% CI)
Any SOC	Any PT	x	xx (xx-xx)	x	xx (xx-xx)	x	xx (xx-xx)	x	xx (xx-xx)	x	xx (xx-xx)	x	xx (xx-xx)
[SOC 1]	Any PT												
	[PT 1]												
	[PT 2]												
[SOC 2]	Any PT												
	[PT 1]												
	[PT 2]												

Notes: N = Number of subjects in the safety population in the given stratum; n = number of subjects with reported event.  
A subject is only counted once per PT.

**Table 54: Number and Percentage of Subjects Experiencing Unsolicited Adverse Events by MedDRA System Organ Class and Preferred Term, Maximum Severity, Relationship, Stratum and Study Group, Safety Population**

MedDRA System Organ Class	MedDRA Preferred Term	Any Incidence		Severity a						Relationship to Vaccination b			
				Mild		Moderate		Severe		Not Related		Related	
		n	%	n	%	n	%	n	%	n	%	n	%
3.75 mcg A/H7N9 (N=X)													
All Subjects (N*=X)													
Any SOC	Any PT	x	xx	x	xx	x	xx	x	xx	x	xx	x	xx
[SOC 1]	Any PT												
	[PT 1]												

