	[PT 2]												
[SOC 2]	Any PT												
	[PT 1]												
	[PT 2]												
[repeat for Strata 1 - 5]													
[repeat for 3.75 mcg A/H7N9 IIV + AS03 (N=X) and All Subjects (N=X)]													
Notes: N = Number of subjects in the safety population in the given study group; N* = Number of subjects in the safety population in the given study group and stratum; n = number of subjects with reported event.													
a For severity, a subject is counted once per preferred term and is summarized according to their highest severity.													
b For relationship, a subject is only counted once per preferred term and is summarized according to their closest relationship.													

**Table 55: Number and Percentage of Subjects Experiencing Non-Serious Related Unsolicited Adverse Events by MedDRA System Organ Class and Preferred Term, Maximum Severity, Stratum and Study Group, Safety Population**

MedDRA System Organ Class	MedDRA Preferred Term	Any Incidence		Severity a					
				Mild		Moderate		Severe	
		n	%	n	%	n	%	n	%
3.75 mcg A/H7N9 (N=X)									
All Subjects (N*=X)									
Any SOC	Any PT	x	xx	x	xx	x	xx	x	xx
[SOC 1]	Any PT	x	xx	x	xx	x	xx	x	xx
	[PT 1]								
	[PT 2]								
[SOC 2]	Any PT								
	[PT 1]								
	[PT 2]								
[repeat for Strata 1 - 5]									
[repeat for 3.75 mcg A/H7N9 IIV + AS03 (N=X) and All Subjects (N=X)]									
Notes: N = Number of subjects in the safety population in the given study group; N* = Number of subjects in the safety population in the given study group and stratum; n = number of subjects with reported event.									
a For severity, a subject is counted once per preferred term and is summarized according to their highest severity.									

**Table 56: Number and Percentage of Subjects Experiencing Unsolicited Adverse Events Within 21 Days Post Study Vaccination by MedDRA System Organ Class and Preferred Term, Day Post Vaccination, Stratum and Study Group, Safety Population**

		2013 A/H7N9 IIV + MF59 (N=X)				2013 A/H7N9 IIV + AS03 (N=X)				2013 A/H7N9 IIV 15 mcg or 45 mcg unadjuvanted (N=X)				2013 A/H7N9 IIV with MF59/AS03 then 2013 A/H7N9 IIV 15 mcg (N=X)				A/H7 IIV Naïve (N=X)				All Subjects (N=X)			

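### SAP 9.3.2 restates the all-cause secondary safety endpoint as vaccine-related only and assigns its result to related-only Table 57

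*SAP*

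**What the plan says.** SAP 3.2.2 lists the endpoint as "Occurrence of all unsolicited non-serious AEs from the time of study vaccination through approximately 21 days after study vaccination". Protocol 3.2.2 uses the same wording, and the matching secondary objective (protocol 3.1.2, SAP 3.1.2) has no causality restriction.

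In SAP 9.3.2, the bullet for Table 57 says that the table presents the results for the secondary safety endpoint, and then sets out that endpoint in quotation marks as "Occurrence of study vaccine-related unsolicited non-serious AEs from the time of study vaccination through approximately 21 days after study vaccination". The Table 57 shell is titled as non-serious and related.

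Protocol 11.6.2 describes the planned analysis: "Non-serious unsolicited AEs will be summarized as number and percentage of subjects reporting at least one event" in each preferred term and system organ class, "cross-tabulated by severity and relationship to study product". Relationship is there a dimension of the table, not a condition for entering it.

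SAP Section 12 states: "This SAP does not include any changes from the analyses described in the protocol".

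**The concern.** The endpoint that 9.3.2 cites appears in neither endpoint section. The word *all* has been replaced by a causality condition, and the table chosen to carry the result applies that condition. A programmer or report author who works from 9.3.2 would report related events as the result of an endpoint that was defined without regard to cause.

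Two things follow. The result filed under the endpoint would depend on the investigator's causality judgement, which the definition does not. And a reader comparing the report with the protocol would find a narrower quantity under the same name, with the SAP stating that nothing had changed.

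**Working it through.** The plan gives no figure to reproduce, so the check compares definitions with table shells.

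**Step 1: what the endpoint requires.** From protocol 3.2.2 and SAP 3.2.2 there are four attributes: unsolicited, non-serious, any relationship, and vaccination through about 21 days (Days 1–22 in the shells).

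**Step 2: what each candidate shell is labelled as.**

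| SAP table | Relationship | Labelled non-serious | Window | Unit |
|---|---|---|---|---|
| 48 (topline), any-unsolicited row | all | no | none stated | subjects |
| 53 | all | no; 9.3.2 says serious or non-serious | none in title | subjects |
| 54 | all, with relationship columns | no | none in title | subjects |
| 55 | related only | yes | none in title | subjects |
| 56 | all | no | 21 days, split 1–8 and 9–22 | subjects |
| 57 | related only | yes | 21 days, split 1–8 and 9–22 | subjects |
| 58 | all | no | columns 1–8 and 9–22 | events |

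Among Tables 53–58, four are all-cause (53, 54, 56, 58) and none of those is labelled non-serious. Two are labelled non-serious (55, 57) and both are related-only. None of the six is labelled as both. Two other displays include all-cause non-serious events but only in part: Table 49 has a 5% threshold, and Table 63 lists moderate or severe events only.

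Against the four attributes, Table 57 meets three and fails on relationship. Table 56 meets three and fails only on the non-serious label.

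**Step 3: direction of the error.** The Table 54 footnote gives the counting rule: "For relationship, a subject is only counted once per preferred term and is summarized according to their closest relationship". Under that rule, in any row and for any scope,

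n(any) = n(related) + n(not related), so n(any) − n(related) = n(not related) ≥ 0.

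A related-only count therefore cannot exceed the all-cause count. The shortfall is the number of subjects whose events were all judged not related. The documents give no AE rates, so its size is unknown.

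**Step 4: combined window.** Tables 56 and 57 count a subject once per preferred term within each period. If a subjects have an event in Days 1–8 and b in Days 9–22, the number with an event in Days 1–22 lies between max(a, b) and a + b. Neither table therefore yields a single Day 1–22 subject count by adding its columns.

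**The case against.** The strongest reply is that the all-cause result is in the report anyway. SAP 6.2.1 says the topline tables are the final analyses of the primary and secondary endpoints. Table 48 is marked as topline, has an all-cause row for unsolicited events and shows serious events in a separate row. Table 57 is not marked as topline. Moreover, SAP 4.5.1 item 5 and protocol 9.1 item 4 define unsolicited AEs as "non-serious AEs occurring from the time of study vaccination through approximately 21 days after study vaccination". On that definition Table 56 already shows the all-cause endpoint by period. Without it, Table 56 differs only by SAEs within 21 days, and protocol 11.6.2 expects few SAEs.

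Most of this stands. A reader might infer that unrelated events go unreported, or that the SAP offers nothing else to use; the documents support neither. Listing 13 and Tables 48, 53, 54, 56 and 58 all include unrelated events. What the reply does not do is repair 9.3.2, which still names Table 57. Nor does the SAP hold to the 4.5.1 definition: Table 53 includes serious events, Tables 55 and 57 add the non-serious qualifier separately, and Listing 13, headed as unsolicited AEs, has a column for SAEs. The scope of Tables 48 and 56 is therefore ambiguous, although the tables themselves are not missing.

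A reader might also infer a deliberate narrowing of the endpoint. SAP 3.2.2 repeats the protocol's wording and Section 12 declares no change, so a drafting error is the better reading. The endpoint is also secondary and descriptive, with no hypothesis test attached (protocol 11.2, SAP 6.8).

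**Conclusion.** The contradiction is real and rests on the text alone: SAP 9.3.2 disagrees with protocol 3.2.2 and with SAP 3.2.2, and points to a table that applies the wrong restriction. If followed, the figure labelled as this endpoint would be a related-only subset, equal to or below the defined quantity. The direction is certain, given one count per subject at the closest relationship. The size cannot be stated.

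The matter is one of designation and labelling, not of lost data. It should be fixed because it concerns a named secondary endpoint, and because no other table is explicitly labelled all-cause, non-serious and Days 1–22.

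**What to change.** 1. In SAP 9.3.2, replace the quoted endpoint with the 3.2.2 wording (all unsolicited non-serious AEs).
2. Remove the endpoint designation from Table 57 and keep the table as a supportive related-only summary.
3. Designate as the endpoint result an all-causality table of non-serious unsolicited AEs with onset on Days 1–22, including a combined Day 1–22 subject count. This can be one added shell, or a non-serious version of Table 56 with an overall column.

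Leave Table 54 unrestricted. Retitling it ("Number and Percentage of Subjects Experiencing Unsolicited Adverse Events by MedDRA System Organ Class and Preferred Term, Maximum Severity, Relationship") as the endpoint table may look simplest, but its shell sets severity and relationship side by side as separate columns and does not cross them. Limiting it to non-serious events on Days 1–22 would also remove any SAEs and later medically attended events from the only all-cause table by severity and relationship. That is a change of content, not of title.

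The cost is one SAP sentence and one shell. The data are already collected.

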#### 9.4. Deaths, Serious Adverse Events and other Significant Adverse Events

The following listings will be presented including Subject ID, age (years), AE description, AE onset date/end date, days post vaccination, reason reported as an SAE, relationship to study product, alternate etiology if not related, outcome, and duration of event in days:

- Deaths and serious adverse events in [Table 59](#);
- Medically attended adverse events in [Table 60](#);
- New onset chronic medical conditions in [Table 61](#);
- Potentially immune mediated medical conditions in [Table 62](#).

A listing of all reported AEs by subject will be presented in [Listing 13](#), sorted by stratum, study group, subject ID, and AE Number.

#### 9.5. Pregnancies

For any subjects in the safety population who became pregnant during the study, every attempt will be made to follow these subjects to completion of pregnancy to document the outcome, including information regarding any complications with pregnancy and/or delivery. [Listing 19](#), [Listing 20](#), [Listing 21](#), [Listing 22](#), and [Listing 23](#) will present any study related pregnancies and their outcomes.

## 9.6. Clinical Laboratory Evaluations

Clinical safety laboratory parameters (WBC, Hgb, PLT, ALT, Bili, Cr) will be collected from each subject prior to study vaccination and approximately 7 days after study vaccination. These evaluations will be performed by the central clinical laboratory. The grading scale for clinical laboratory evaluations is presented in [Table 12](#). Clinical laboratory evaluations assessed on Day 1 prior to the study vaccination will be considered as baseline.

The distribution of laboratory results by severity, study day, study group, and stratum will be presented in [Table 66](#), [Table 67](#), [Table 68](#), [Table 69](#), [Table 73](#), [Table 74](#), [Table 75](#), and [Table 76](#). Descriptive statistics including mean, standard deviation, median, maximum and minimum values by each study day will be summarized for each parameter and for the change from baseline for each parameter in [Table 70](#), [Table 71](#), [Table 72](#), [Table 73](#), [Table 77](#), [Table 78](#), [Table 79](#), and [Table 80](#). Box plots illustrating the change from baseline for each laboratory parameter will be presented in [Figure 32](#), [Figure 33](#), [Figure 34](#), [Figure 35](#), [Figure 36](#), and [Figure 37](#). Subject visits with abnormal laboratory results, mild severity or greater, will be presented in [Table 64](#) and [Table 65](#) for chemistry and hematology parameters, respectively.

A complete listing of individual clinical laboratory results will be presented in [Listing 14](#) and [Listing 15](#) for chemistry and hematology, respectively, sorted by stratum, study group, subject ID, parameter, and visit.

## 9.7. Vital Signs and Physical Evaluations

Oral temperature, systolic blood pressure, diastolic blood pressure, and pulse will be assessed prior to study vaccination on Day 1 and these results will be considered as baseline. Additional measurements of vital signs may be taken on Day 2, Day 4, and Day 8 if indicated. The grading scale for vital sign evaluations is presented in [Table 11](#). Summaries of vital signs by maximum severity will be tabulated for baseline and post-baseline measurements, grouped by stratum and study group and presented in [Table 80](#), [Table 81](#), [Table 82](#), [Table 83](#), and [Table 84](#). A listing of vital signs will be presented in [Listing 16](#).

Targeted physical examinations will be performed, if indicated, based on a subject's medical history. A listing of physical exam findings will be presented in [Listing 17](#).

## 9.8. Concomitant Medications

Concomitant medications will be collected for the 30 days prior to study vaccination through 21 days after study vaccination. Concomitant medications will be coded to the ATC using the WHO Drug Dictionary. The use of prior and concomitant medications taken during the study will be recorded on the eCRFs. A by-subject listing of concomitant medications during the study will be summarized by ATC1 code, ATC2 code, stratum, and study group for the safety population in [Table 85](#).

## 10. REPORTING CONVENTIONS

P-values  $\geq 0.001$  and  $\leq 0.999$  will be reported to 3 decimal places; p-values less than 0.001 will be reported as “<0.001”; p-values greater than 0.999 will be reported as “> 0.999“. The mean, standard deviation, and any other statistics other than quantiles, will be reported to one decimal place greater than the original data. Quantiles, such as median, or minimum and maximum will use the same number of decimal places as the original data. Proportions will be presented as two decimal places; values <0.01 will be presented as “<0.01”. Percentages will be reported to the nearest whole number; non-zero values < 1% will be presented as “<1”; values greater than 99% but less than 100% will be presented as >99. Estimated parameters, not on the same scale as raw observations (e.g. regression coefficients) will be reported to 3 significant figures.

